10. MANAGEMENT AND REPORTING OF ADVERSE EVENTS/ADVERSE REACTIONS

The reference document to use during this observational study is the SmPC for the Sutent® range, version no.: 001-01/14.

REQUIREMENTS

The table below summarizes the requirements for recording safety events on the electronic data capture and for reporting safety events on the non-interventional study (NIS) adverse event monitoring (AEM) Report Form to Pfizer Safety. These requirements are delineated for three types of events: (1) serious adverse events (SAEs); (2) non-serious AEs (as applicable); and (3) scenarios involving drug exposure, including exposure during pregnancy, exposure during breast feeding, medication error, overdose, misuse, extravasation, and occupational exposure. These events are defined in the section “Definitions of safety events”.

Safety event	Recorded on the electronic data capture	Reported on the NIS AEM Report Form to Pfizer Safety within 24 hours of awareness
SAE	All	All
Non-serious AE	All	
10.1. Poential reiks (PGR SUTENT V16.0)
 
Carcinogénicity Potential Other cardiac events: Trouble of the conduction, Ischemic events Tachycardia Retinal abruption
 
Missing important informations (PGR SUTENT V16.0)
 
Pédiatric population Pregnancy and lactation Severe hepatic insufficiency Cardiac insufficiency

Safety event	Recorded on the electronic data capture	Reported on the NIS AEM Report Form to Pfizer Safety within 24 hours of awareness
Scenarios involving exposure to a drug under study, including exposure during pregnancy, exposure during breast feeding, medication error, overdose, misuse, extravasation; lack of efficacy; and occupational exposure	All (regardless of whether associated with an AE), except occupational exposure	All (regardless of whether associated with an AE)

For each AE, the investigator must pursue and obtain information adequate both to determine the outcome of the adverse event and to assess whether it meets the criteria for classification as a SAE (see section "Serious Adverse Events" below)

Safety events listed in the table above must be reported to Pfizer within 24 hours of awareness of the event by the investigator **regardless of whether the event is determined by the investigator to be related to a drug under study**.

In particular, if the SAE is fatal or life-threatening, notification to Pfizer must be made immediately, irrespective of the extent of available event information. This timeframe also applies to additional new (follow-up) information on previously forwarded safety event reports. In the rare situation that the investigator does not become immediately aware of the occurrence of a safety event, the investigator must report the event within 24 hours after learning of it and document the time of his/her first awareness of the events.

For safety events that are considered serious or that are identified in the far right column of the table above that are reportable to Pfizer within 24 hours of awareness, the investigator is obligated to pursue and to provide any additional information to Pfizer in accordance with this 24-hour timeframe. In addition, an investigator may be requested by Pfizer to obtain specific follow-up information in an expedited fashion. This information is more detailed than that recorded on the electronic data capture. In general, this will include a description of the adverse event in sufficient detail to allow for a complete medical assessment of the case and independent determination of possible causality. Any information relevant to the event, such as concomitant medications and illnesses must be provided. In the case of a patient death, a summary of available autopsy findings must be submitted as soon as possible to Pfizer or its designated representative.

Reporting period

For each patient, the safety event reporting period begins at the time of the patient's first dose of Sutent or the time of the patient's informed consent signed date if s/he is already exposed to Sutent, and lasts through the end of the observation period of the study, which must include at least 28 calendar days following the last administration of a drug under study; a report must be submitted to Pfizer Safety (or its designated representative) for any of the types of safety events listed in the table above occurring during this period.

If a patient was administered a drug under study on the last day of the observation period, then the reporting period should be extended for 28 calendar days following the end of observation.

Most often, the date of informed consent is the same as the date of enrollment. In some situations, there may be a lag between the dates of informed consent and enrollment. In these instances, if a patient provides informed consent but is never enrolled in the study (e.g., patient changes his/her mind about participation, the reporting period ends on the date of the decision to not enroll the patient.

If the investigator becomes aware of a SAE occurring at any time after completion of the study and s/he considers the SAE to be related to *<the named drugs under study>*, the SAE also must be reported to Pfizer Safety.

Causality assessment

The investigator is required to assess and record the causal relationship. For all AEs, sufficient information should be obtained by the investigator to determine the causality of each adverse event. For AEs with a causal relationship to Sutent, follow-up by the investigator is required until the event and/or its sequelae resolve or stabilize at a level acceptable to the investigator, and Pfizer concurs with that assessment.

An investigator's causality assessment is the determination of whether there exists a reasonable possibility that Sutent caused or contributed to an adverse event. If the investigator's final determination of causality is "unknown" and s/he cannot determine whether Sutent caused the event, the safety event must be reported within 24 hours.

If the investigator cannot determine the etiology of the event but s/he determines that Sutent did not cause the event, this should be clearly documented on the electronic data capture and the NIS AEM Report Form.

DEFINITIONS OF SAFETY EVENTS

Adverse events

An AE is any untoward medical occurrence in a patient administered a medicinal product. The event need not necessarily have a causal relationship with the product treatment or usage. Examples of adverse events include but are not limited to:

- Abnormal test findings (see below for circumstances in which an abnormal test finding constitutes an adverse event);
- Clinically significant symptoms and signs;
- Changes in physical examination findings;
- Hypersensitivity;
- Progression/worsening of underlying disease; *<(Omit for Oncology and HIV studies)>*
- Lack of efficacy;
- Drug abuse;
- Drug dependency.

Additionally, for medicinal products, they may include the signs or symptoms resulting from:

- Drug overdose;
- Drug withdrawal;
- Drug misuse;
- Off-label use;
- Drug interactions;
- Extravasation;
- Exposure during pregnancy;
- Exposure during breast feeding;
- Medication error;
- Occupational exposure.

Abnormal test findings

The criteria for determining whether an abnormal objective test finding should be reported as an adverse event are as follows:

- Test result is associated with accompanying symptoms, and/or
- Test result requires additional diagnostic testing or medical/surgical intervention, and/or
- Test result leads to a change in study dosing or discontinuation from the study, significant additional concomitant drug treatment, or other therapy, and/or
- Test result is considered to be an adverse event by the investigator or sponsor.

Merely repeating an abnormal test, in the absence of any of the above conditions, does not constitute an adverse event. Any abnormal test result that is determined to be an error does not require reporting as an adverse event.

Serious adverse events

A serious adverse event is any untoward medical occurrence in a patient administered a medicinal or nutritional product (including pediatric formulas) at any dose Sutent:

- Results in death;
- Is life-threatening;
- Requires inpatient hospitalization or prolongation of hospitalization (see below for circumstances that do not constitute adverse events);
- Results in persistent or significant disability/incapacity (substantial disruption of the ability to conduct normal life functions);
- Results in congenital anomaly/birth defect.

Progression of the malignancy under study (including signs and symptoms of progression) should not be reported as a serious adverse event unless the outcome is fatal within the safety reporting period. Hospitalization due to signs and symptoms of disease progression should not be reported as a serious adverse event. If the malignancy has a fatal outcome during the study or within the safety reporting period, then the event leading to death must be recorded as an adverse event and as a serious adverse event with severity Grade 5.”

Medical and scientific judgment is exercised in determining whether an event is an important medical event. An important medical event may not be immediately life-threatening and/or result in death or hospitalization. However, if it is determined that the event may jeopardize the patient or may require intervention to prevent one of the other outcomes listed in the definition above, the important medical event should be reported as serious.

Examples of such events are intensive treatment in an emergency room or at home for allergic bronchospasm; blood dyscrasias or convulsions that do not result in hospitalization; or development of drug dependency or drug abuse.

Additionally, any suspected transmission via a Pfizer product of an infectious agent, pathogenic or non-pathogenic, is considered serious. The event may be suspected from clinical symptoms or laboratory findings indicating an infection in a patient exposed to a Pfizer product. The terms “suspected transmission” and “transmission” are considered synonymous. These cases are considered unexpected and handled as serious expedited cases by PV personnel. Such cases are also considered for reporting as product defects, if appropriate.

Hospitalization

Hospitalization is defined as any initial admission (even if less than 24 hours) to a hospital or equivalent healthcare facility or any prolongation to an existing admission. Admission also includes transfer within the hospital to an acute/intensive care unit (e.g., from the psychiatric wing to a medical floor, medical floor to a coronary care unit, neurological floor to a tuberculosis unit). An

emergency room visit does not necessarily constitute a hospitalization; however, an event leading to an emergency room visit should be assessed for medical importance.

Hospitalization in the absence of a medical AE is not in itself an AE and is not reportable. For example, the following reports of hospitalization without a medical AE are not to be reported.

- Social admission (e.g., patient has no place to sleep)
- Administrative admission (e.g., for yearly exam)
- Optional admission not associated with a precipitating medical AE (e.g., for elective cosmetic surgery)
- Hospitalization for observation without a medical AE
- Admission for treatment of a pre-existing condition not associated with the development of a new AE or with a worsening of the pre-existing condition (e.g., for work-up of persistent pre-treatment lab abnormality)
- Protocol-specified admission during clinical study (e.g., for a procedure required by the study protocol)

Scenarios necessitating reporting to Pfizer Safety within 24 hours

Scenarios involving exposure during pregnancy, exposure during breastfeeding, medication error, overdose, misuse, extravasation, lack of efficacy, and occupational exposure are described below.

Exposure during pregnancy

An exposure during pregnancy (EDP) occurs if:

1. A female becomes, or is found to be, pregnant either while receiving or having been exposed to (e.g., environmental) Sutent or the female becomes, or is found to be, pregnant after discontinuing and/or being exposed to Sutent (maternal exposure).

An example of environmental exposure would be a case involving direct contact with a Pfizer product in a pregnant woman (e.g., a nurse reports that she is pregnant and has been exposed to chemotherapeutic products).

2. A male has been exposed, either due to treatment or environmental exposure Sutent prior to or around the time of conception and/or is exposed during the partner pregnancy (paternal exposure).

As a general rule, prospective and retrospective exposure during pregnancy reports from any source are reportable irrespective of the presence of an associated AE and the procedures for SAE reporting should be followed.

If a study participant or study participant's partner becomes, or is found to be, pregnant during the study participant's treatment with Sutent, this information must be submitted to Pfizer, irrespective of whether an adverse event has occurred using the NIS AEM Report Form and the EDP Supplemental Form.

In addition, the information regarding environmental exposure to Sutent in a pregnant woman (e.g., a subject reports that she is pregnant and has been exposed to a cytotoxic product by inhalation or spillage) must be submitted using the NIS AEM Report Form and the EDP supplemental form. This must be done irrespective of whether an AE has occurred.

Information submitted should include the anticipated date of delivery (see below for information related to termination of pregnancy).

Follow-up is conducted to obtain general information on the pregnancy; in addition, follow-up is conducted to obtain information on EDP outcome for all EDP reports with pregnancy outcome unknown. A pregnancy is followed until completion or until pregnancy termination (e.g., induced abortion) and Pfizer is notified of the outcome. This information is provided as a follow up to the initial EDP report. In the case of a live birth, the structural integrity of the neonate can be assessed at the time of birth. In the event of a termination, the reason(s) for termination should be specified and, if clinically possible, the structural integrity of the terminated fetus should be assessed by gross visual inspection (unless pre-procedure test findings are conclusive for a congenital anomaly and the findings are reported).

If the outcome of the pregnancy meets the criteria for an SAE (e.g., ectopic pregnancy, spontaneous abortion, intrauterine fetal demise, neonatal death, or congenital anomaly [in a live born, a terminated fetus, an intrauterine fetal demise, or a neonatal death]), the procedures for reporting SAEs should be followed.

Additional information about pregnancy outcomes that are reported as SAEs follows:

- Spontaneous abortion includes miscarriage and missed abortion;
- Neonatal deaths that occur within 1 month of birth should be reported, without regard to causality, as SAEs. In addition, infant deaths after 1 month should be reported as SAEs when the investigator assesses the infant death as related or possibly related to exposure to investigational product

Additional information regarding the exposure during pregnancy may be requested. Further follow-up of birth outcomes will be handled on a case-by-case basis (e.g., follow-up on preterm infants to identify developmental delays).

In the case of paternal exposure, the study participant will be provided with the Pregnant Partner Release of Information Form to deliver to his partner. It must be documented that the study participant was given this letter to provide to his partner.

Exposure during breastfeeding

Scenarios of exposure during breastfeeding must be reported, irrespective of the presence of an associated AE. An exposure during breastfeeding report is not created when a Pfizer drug specifically approved for use in breastfeeding women (e.g., vitamins) is administered in accord with authorized use. However, if the infant experiences an AE associated with such a drug's administration, the AE is reported together with the exposure during breastfeeding.

Medication error

A medication error is any unintentional error in the prescribing, dispensing or administration of a medicinal product that may cause or lead to inappropriate medication use or patient harm while in the control of the health care professional, patient, or consumer. Such events may be related to professional practice, health care products, procedures, and systems including: prescribing; order communication; product labeling, packaging, and nomenclature; compounding; dispensing; distribution; administration; education; monitoring; and use.

Medication errors include:

- Near misses, involving or not involving a patient directly (e.g., inadvertent/erroneous administration, which is the accidental use of a product outside of labeling or prescription on the part of the healthcare provider or the patient/consumer);
- Confusion with regard to invented name (e.g., trade name, brand name).

The investigator must submit the following medication errors to Pfizer, irrespective of the presence of an associated AE/SAE :

- Medication errors involving patient exposure to the product, whether or not the medication error is accompanied by an AE.
- Medication errors that do not involve a patient directly (e.g., potential medication errors or near misses). When a medication error does not involve patient exposure to the product the following minimum criteria constitute a medication error report:
 - An identifiable reporter;
 - A suspect product;
 - The event medication error.

Overdose, Misuse, Extravasation

Reports of overdose, misuse, and extravasation associated with the use of a Pfizer product are reported to Pfizer by the investigator, irrespective of the presence of an associated AE/SAE.

Lack of Efficacy

Reports of lack of efficacy to a Pfizer product are reported to Pfizer by the investigator, irrespective of the presence of an associated AE/SAE or the indication for use of the Pfizer product.

Occupational Exposure

Reports of occupational exposure to a Pfizer product are reported to Pfizer by the investigator, irrespective of the presence of an associated AE/SAE.

Communication problems

In case of prohibition or restriction (eg clinical hold) by a competent authority in any region of the world, or if the investigator is aware of any new information that may influence the evaluation of the benefits and risks of Sutent, Pfizer must be informed immediately.

In addition, Pfizer will inform the investigator immediately of any urgent safety measure taken by the investigator to protect patients in the trial against any immediate danger, and any serious violation of the Memorandum of NI study in which the investigator is aware.

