6.6 Description of adverse events

Study population: Population of followed-up patients

The number of AEs, the number and percentage of patients with at least one AE will be described by group for the following event categories:

- All AEs by system organ class,
- All AEs likely to be related to the study drug ('Yes' or Missing response method) by system organ class,
- All serious AEs by system organ class,
- All serious AEs likely to be related to the study drug ('Yes' or Missing response method) by organ class,

The AEs will be described according to severity, action taken regarding the study treatment, and progression.

AEs reported during the study will be coded using the MedDRA dictionary, version 20.0.

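### Protocol section 10 contradicts itself on whether non-fatal progression is an adverse event, and SAP 6.6 has no rule for such records

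*Protocol*

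**What the plan says.** **AE definition (protocol section 10, Adverse events).** The examples include "Progression/worsening of underlying disease; *<(Omit for Oncology and HIV studies)>" and, as a separate item, "Lack of efficacy".

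**Requirements table (protocol section 10).** Every non-serious AE is recorded on the electronic data capture. For the row that covers exposure scenarios and lack of efficacy, the recording entry is "All (regardless of whether associated with an AE), except occupational exposure", and all such scenarios go to the sponsor's safety department within 24 hours. The later Lack of Efficacy paragraph repeats the duty: "Reports of lack of efficacy to a Pfizer product are reported to Pfizer by the investigator, irrespective of the presence of an associated AE/SAE".

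**SAE text (protocol section 10, Serious adverse events).** Progression of the malignancy, with its signs and symptoms, "should not be reported as a serious adverse event unless the outcome is fatal within the safety reporting period". Also: "Hospitalization due to signs and symptoms of disease progression should not be reported as a serious adverse event". A malignancy with a fatal outcome must be recorded as both an AE and a Grade 5 SAE.

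**SAP.** Section 2.4 names adverse events as an endpoint. Section 6.6 states: "The number of AEs, the number and percentage of patients with at least one AE will be described by group", for all AEs, related AEs, serious AEs and related serious AEs. A missing causality answer counts as related. No sentence deals with progression or lack-of-efficacy terms.

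**Where progression is captured otherwise.** Both case report forms have a progression page (protocol Appendices 5 and 6). SAP 6.4 and 6.5 analyse progression-free survival by Kaplan-Meier in each group.

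**The concern.** This is a metastatic renal cancer study, so the bullet and its bracketed note give opposite directions. A site that follows the bullet records each progression as a non-serious AE. A site that follows the note records none. The SAE carve-out does not decide the matter, because it governs serious events only.

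At stake is the meaning of the descriptive AE tables. If some sites log progression, the total number of AEs, and possibly the number of patients with at least one AE, would mix disease outcome with tolerability, to a degree that depends on the site. A progression record with a blank causality field would also enter the related-AE table. Nothing is gained in return, since progression has its own page and its own analysis.

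**Working it through.** The documents state no AE count and no number of progressions recorded as AEs, so there is no plan figure to reproduce. The check has two parts.

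**1. Does any other text settle the question?**

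- The bullet lists progression; the note beside it says to omit it. Another unfilled placeholder (for the study drug names, under Reporting period) suggests unfinished template text rather than a decision.
- The requirements table sends all non-serious AEs to the electronic record but does not say whether progression is one.
- The SAE text removes non-fatal progression, its signs and symptoms, and resulting hospitalization from SAEs. It is silent on non-serious AEs.
- Deleting the bullet alone would leave other routes open. Clinically significant symptoms and signs are an AE example. Under Abnormal test findings, a result that leads to other therapy qualifies as an AE, which could describe a scan showing progression. Lack of efficacy is both an AE example and a scenario to be recorded electronically.
- On the Case annual-visit form, progression directs the site to the progression visit page, and only intolerance directs it to the AE form. The Control form has a progression page but no such prompts, so recording could differ by group as well as by site.

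No passage resolves the contradiction.

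**2. How large could the effect be?** This is for scale only.

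Inputs: 80 Controls and 40 Cases (SAP 2.5); 36 months of follow-up (protocol 8.1.4); resistance to VEGF-targeted treatment after 6 to 15 months (protocol section 6), *assumed* here to be the range of median time to progression in Controls, with exponential times; recurrence in almost half of complete-remission patients after withdrawal (protocol abstract), *assumed* as 50% of Cases, range 25% to 75%.

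Controls progressing by 36 months, s = 1 − 0.5^(36/m):

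- m = 15: 1 − 0.5^2.4 = 0.811; × 80 = 64.8, about 65
- m = 6: 1 − 0.5^6 = 0.984; × 80 = 78.8, about 79

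Cases: 0.50 × 40 = 20 (0.25 × 40 = 10 to 0.75 × 40 = 30).

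If every progression were logged as one AE, that adds 0.81 to 0.98 records per Control and 0.25 to 0.75 per Case. With k other AEs per patient, the share of AE records that are progressions is s/(s + k):

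| Other AEs per patient (k) | Controls | Cases (50%) |
|---|---|---|
| 1 | 45% to 50% | 33% |
| 3 | 21% to 25% | 14% |
| 5 | 14% to 16% | 9% |
| 10 | 7.5% to 9% | 5% |

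The documents give no value for k, so the applicable row is unknown.

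**The case against.** A reader might infer that expected progressions will enter the AE tables and swamp the Control column. The documents do not support that, for several reasons.

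- The note itself says to omit the item, and the Case form steers progression away from the AE form. The text is contradictory; it is not an instruction to record.
- The 65 to 79 figure counts progressions, not distortion of a table. It treats time to resistance as median time to progression and ignores dropout and death before progression.
- The row for at least one AE counts each patient once, so it moves only for patients with no other AE.
- Cases progress too, so both columns are affected.
- The tables are descriptive, with no p-value column, and the SAP Annex 1 layout by preferred term would show coded progression on its own line.
- Non-fatal progression is already excluded from SAEs.
- No passage equates lack of efficacy with RECIST progression.
- The two columns are not a clean tolerability contrast in any case: reporting starts at first dose for Controls but at consent for patients already on Sutent.

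All of this stands, and it limits the size and certainty of the consequence. It does not remove the contradiction. A preferred-term line still feeds the totals and the system-organ-class counts, and it cannot show which sites chose not to record.

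**Conclusion.** The point holds as an unresolved contradiction in the AE definition, matched by a missing counting rule in the SAP. Inconsistent recording of non-fatal progression is possible, not certain. If it occurs, it inflates descriptive AE counts, probably more in Controls: under the assumptions above, more records are added per Control than per Case throughout the range, provided both groups log progression equally. The share of the Control total could be anywhere from about 7.5% to 50% if all progressions were logged, and less if only some sites do so.

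The effect is confined to a descriptive safety endpoint. The primary comparison of patient characteristics does not use AE counts and is unaffected. The change is still worth making, because it alters what sites record and what a named endpoint counts, at almost no cost.

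**What to change.** **Protocol section 10**

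- Delete the progression bullet together with its template note.
- Reconcile the requirements table, the AE definition (including abnormal test findings), the SAE text and the Lack of Efficacy paragraph. Non-fatal RECIST progression, its signs and symptoms, and lack of efficacy shown only by progression should be handled the same way throughout: captured on the progression page, not as AEs.
- State in the table's lack-of-efficacy row where such a case is recorded electronically.
- Leave unchanged the rule that fatal progression is an AE and a Grade 5 SAE, and the reporting of lack of efficacy to the sponsor's safety department.

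**SAP 6.6**

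- Exclude progression and lack-of-efficacy terms from the AE totals, or show them on a separate line.
- Show fatal progression on its own line in the SAE table.

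**Cost.** A wording change in one protocol section and one filtering rule in the SAP, which also deals with records already coded. AE counts become slightly lower. No progression data are lost, because the progression pages and the progression-free survival analyses remain.
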